3.4 DOSING DELAYS AND MODIFICATIONS

3.4.1 General guidance

If, in the opinion of the investigator, a toxicity is considered to be due solely to one drug (e.g. hand-foot syndrome secondary to capecitabine, neurotoxicity due to oxaliplatin), the dose of the other drug does not require modification.

When, at the beginning of a treatment cycle, treatment delay related to either oxaliplatin or capecitabine treatment alone is indicated, both oxaliplatin and capecitabine treatment should be delayed (except in the case of oxaliplatin-related neurological adverse events). Treatment should only be restarted when the requirements for restarting both oxaliplatin and capecitabine are met, or when oxaliplatin has to be discontinued but the requirements for restarting capecitabine alone are met.

Dose modifications for isolated abnormal hematologic lab values will be based on hematological parameters at start of a treatment cycle. There is no scheduled sampling during a treatment cycle and thus, no scheduled collection of nadir values.

If capecitabine must be discontinued permanently due to toxicity, the patient may continue on oxaliplatin alone. If the patient has SD or better on study, and both capecitabine and oxaliplatin are stopped prematurely for toxicity, the PI may consider continuing pembrolizumab.

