3.4.2 Dose Modifications for Hematologic Toxicity

Capecitabine is not expected to worsen or unduly prolong episodes of neutropenia/granulocytopenia. The next treatment cycle can only start if hematologic toxicity has recovered to grade ≤ 1 . No dose reductions or interruptions will be required for anemia (non-hemolytic) as it can be satisfactorily managed by transfusions.

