6 DATA COLLECTION AND EVALUATION

6.1 DATA COLLECTION

The PI will be responsible for overseeing entry of data into an in-house password protected electronic system (C3D) and Labmatrix ensuring data accuracy, consistency and timeliness. The principal investigator, associate investigators/research nurses and/or a contracted data manager will assist with the data management efforts. All data obtained during the conduct of the protocol will be kept in secure network drives or in approved alternative sites that comply with NIH security standards. Primary and final analyzed data will have identifiers so that research data can be attributed to an individual human subject participant.

All adverse events, including clinically significant abnormal findings on laboratory evaluations, regardless of severity, will be followed until return to baseline or stabilization of event.

Document AEs from the first study intervention, Study Day 1 of Cycle 1 through 30 days after the subject received the last study drug administration. Beyond 30 days after the last intervention, only adverse events which are serious and related to the study intervention need to be recorded.

An abnormal laboratory value will be recorded in the database as an AE **only** if the laboratory abnormality is characterized by any of the following:

- Results in discontinuation from the study
- Is associated with clinical signs or symptoms
- Requires treatment or any other therapeutic intervention
- Is associated with death or another serious adverse event, including hospitalization.
- Is judged by the Investigator to be of significant clinical impact
- If any abnormal laboratory result is considered clinically significant, the investigator will provide details about the action taken with respect to the test drug and about the patient's outcome.

Grade 1 adverse events will not be recorded.

End of study procedures: Data will be stored according to HHS, FDA regulations and NIH Intramural Records Retention Schedule as applicable.

Loss or destruction of data: Should we become aware that a major breach in our plan to protect subject confidentiality and trial data has occurred, this will be reported expeditiously per requirements in section [7.2.1](#).

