In addition to evaluation of the proportion of patients that are progression-free at 5 months, the progression-free survival for patients will also be analyzed via a Kaplan-Meier curve. This curve will be compared informally to other published results in similar patients. As well, the overall response rate will be reported, and the overall survival will be reported using a Kaplan-Meier curve. It is anticipated that up to 10 patients per year will be able to enroll onto this protocol. Thus, it is expected that accrual of up to 17 total patients can be completed in approximately 2 years. In order to allow for a small number of unevaluable patients, the accrual ceiling will be set at 19 patients.

To evaluate the response rate, proportion of patients obtaining CR and PR per RECIST 1.1 criteria of all evaluable patients will be analyzed.

To address safety, tolerability and feasibility of Pembrolizumab in combination with CAPOX chemotherapy, adverse events will be tabulated by grade according to CTCAE and analyzed and reported descriptively.

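### The laboratory adverse-event rule names neither CTCAE grade nor a study-drug delay or reduction, so recording an asymptomatic Grade 3-4 count that changes CAPOX dosing is left to the investigator's reading

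*Combined protocol and SAP*

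**What the plan says.** **Recording.** Section 6.1 states: "An abnormal laboratory value will be recorded in the database as an AE". The word that follows, set in bold, makes the conditions exclusive. Four of them are "Results in discontinuation from the study", "Is associated with clinical signs or symptoms", "Requires treatment or any other therapeutic intervention" and "Is associated with death or another serious adverse event, including hospitalization". A fifth leaves it to the investigator to decide whether the value has significant clinical impact. A last bullet asks what was done with the test drug and how the patient fared, but only for a result already considered clinically significant.

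**Dosing.** Section 3.4.1: "Dose modifications for isolated abnormal hematologic lab values will be based on hematological parameters at start of a treatment cycle". The same section says that no samples are scheduled within a cycle, so nadir values are not collected. Section 3.4.2: "The next treatment cycle can only start if hematologic toxicity has recovered to grade" 1 or lower. The table in Section 3.4.3 cuts both capecitabine and oxaliplatin at the first Grade 3 or Grade 4 neutrophil or platelet count, and stops treatment after repeat occurrences.

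**Analysis.** Section 1.1.2 makes safety, tolerability and feasibility a secondary objective. Section 8 addresses it in one sentence: "adverse events will be tabulated by grade according to CTCAE and analyzed and reported descriptively". It plans no table of graded laboratory values, dose delays, dose reductions or dose intensity.

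**The concern.** The protocol treats certain blood counts as serious enough to hold a cycle or reduce two drugs, yet the recording rule does not list either consequence as a reason to enter the count as an adverse event. Grade is not a reason either. Myelosuppression is often found on a routine count in a patient who feels well, and those are the values the Day 1 sampling will show.

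At stake is the secondary objective. Counts that force delays and reductions are direct evidence on tolerability and feasibility. If they enter the database only when someone chooses to enter them, two patients with the same count and the same dose change can be reported differently, and the error in the Grade 3-4 rate runs downwards. This is separate from Section 6.1's decision not to record Grade 1 events, because it concerns higher grades.

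**Working it through.** There is no stated figure to reproduce, because the point rests on the text of a rule. The check has two parts.

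**1. Take one case through the Section 6.1 list.** The case is a Day 1 neutrophil or platelet count of Grade 3 or 4, in a patient without symptoms who needs no supportive treatment and is not admitted.

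| Section 6.1 condition | Is recording compelled? |
|---|---|
| "Results in discontinuation from the study" | No. The cycle is delayed and later doses are reduced, but the patient stays on study. |
| "Is associated with clinical signs or symptoms" | No, by construction of the case. |
| "Requires treatment or any other therapeutic intervention" | Unclear. The text neither includes nor excludes a change in study-drug dose. |
| "Is associated with death or another serious adverse event, including hospitalization" | No, by construction of the case. |
| Investigator's judgment of clinical impact | Permitted, not required. |
| Last bullet (action taken with the drug) | Not a trigger. It applies once the result is already held to be significant. |

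The first row matters even when treatment ends. Section 3.6.1 (removal from protocol therapy) and Section 3.6.2 (off study) are separate lists. Delayed recovery from toxicity is on the first and not on the second. A permanent stop under the Section 3.4.3 table therefore does not expressly meet a trigger worded in terms of the study.

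For the same case, Section 3.4.3 prescribes:

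- First Grade 3: capecitabine to 75% of the original dose; oxaliplatin from 130 to 100 mg/m², 100/130 = 76.9% of the starting dose.
- First Grade 4: capecitabine to 50%; oxaliplatin from 130 to 85 mg/m², 85/130 = 65.4% of the starting dose.

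So the dosing rule is mandatory and substantial, while the recording rule for the same value is optional.

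**2. Size of one omission.** Inputs: Section 6.3.1 makes every patient evaluable for toxicity from the first pembrolizumab dose. Section 8 sets a target of 17 patients and an accrual ceiling of 19. If k of N treated patients have a Grade 3-4 event and one patient's only such event is not recorded, the reported rate falls by

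k/N − (k − 1)/N = 1/N.

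- N = 19: 1/19 = 5.3 percentage points.
- N = 17: 1/17 = 5.9 percentage points.
- If accrual stops after the first 10 patients: 1/10 = 10.0 percentage points.

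The step does not depend on k, so no event rate has to be assumed. The number of such patients cannot be derived from the documents.

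**The case against.** The best defence is that two conditions can already catch these values. Holding a cycle or cutting two drugs because of a count may fairly be called a therapeutic intervention, and "Requires treatment or any other therapeutic intervention" is broad. Failing that, an investigator who has just reduced two drugs because of a count would find it hard to call that count clinically unimportant. The last bullet suggests the authors expected significant laboratory values to be linked to action on the drug. Section 7.4 adds regular team discussion of each patient and review of adverse-event data by the principal investigator. The counts themselves are kept: the Study Calendar (Section 3.5) places blood count and chemistry within 48 hours before study drug in each cycle. Recording only laboratory values thought to matter is also a common choice in a small, descriptive, single-arm trial.

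Much of this stands. A reader might infer that such counts meet none of the triggers and will be missing from the results. The documents do not support that, because both routes are open. Nor are data lost: the grades can be recovered from the laboratory record.

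What remains is that neither route is compulsory. The text does not say whether a dose change counts as an intervention, and clinical impact is a matter of judgment. The review in Section 7.4 covers adverse-event and response data, so it does not by itself bring in a value never entered as an adverse event. Section 8 does not use the stored counts for safety.

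**Conclusion.** The point holds as a gap in what must be recorded. Under Section 6.1, an asymptomatic Grade 3-4 neutrophil or platelet count that delays a cycle or cuts both CAPOX drugs need not appear as an adverse event, and Section 8 has no other table in which it would appear. The Grade 3-4 rate can therefore be too low and can vary with the recorder.

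The supportable size is 5.3 to 5.9 percentage points per omitted patient at 19 to 17 treated patients. It assumes that the patient has no other recorded Grade 3-4 event. A reader might be tempted to go further and suppose, say, 2 to 5 such patients (2/19 = 11% to 5/19 = 26% of all treated patients). The documents give no basis for those counts. Such a figure would also assume that every such value goes unrecorded, and it would not be a share of the patients with Grade 3-4 toxicity, whose number is unknown.

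The primary endpoint is unaffected, and Section 8 sets no safety threshold or stopping rule that depends on this rate. The case for acting is that a discretionary rule for a stated secondary objective can be made objective at little cost.

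**What to change.** **Section 6.1.** Add two triggers to the list:

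1. any laboratory abnormality of CTCAE Grade 3 or higher;
2. any laboratory abnormality that leads to delay, interruption, reduction or discontinuation of any study drug.

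The second settles whether a dose change counts as an intervention. It also captures a Grade 2 count that only holds up the next cycle, and a permanent stop of treatment in a patient who stays on study.

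**Section 8.** Add a table of hematology and chemistry by worst CTCAE grade per patient, computed directly from the laboratory results. Because it draws on stored values, it also covers patients already treated and does not depend on adverse-event entry.

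**Cost.** Two lines in Section 6.1, one sentence and one table in Section 8, some extra adverse-event entries, and a reported toxicity rate that will probably look somewhat higher. No additional visit or blood sample is needed, and no dosing rule changes.

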1. INTRODUCTION

1.1 STUDY OBJECTIVES

1.1.1 Primary Objective:

- To determine the 5-month PFS of Pembrolizumab in combination with capecitabine and oxaliplatin chemotherapy (CAPOX) in patients with advanced biliary tract carcinoma.

1.1.2 Secondary Objectives:

- To determine the safety, tolerability and feasibility of Pembrolizumab in combination with capecitabine and oxaliplatin chemotherapy (CAPOX) in patients with advanced biliary tract carcinoma.
- To evaluate the response rate and overall survival in patients with advanced biliary tract cancer during and following treatment with Pembrolizumab in combination with capecitabine and oxaliplatin chemotherapy (CAPOX) in patients with advanced biliary tract carcinoma.

1.1.3 Exploratory Objectives:

- To measure changes in PDL1 expression in the tumors of patients with advanced biliary tract cancer following treatment with capecitabine and oxaliplatin chemotherapy (CAPOX) in patients with advanced biliary tract carcinoma.
- To measure changes in immune parameters in the peripheral blood and tumors in patients with advanced biliary tract cancer following treatment with Pembrolizumab in combination with capecitabine and oxaliplatin chemotherapy (CAPOX) in patients with advanced biliary tract carcinoma.

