Dosing interruptions are permitted in the case of medical / surgical events or logistical reasons not related to study therapy (e.g., elective surgery, unrelated medical events, patient vacation, and/or holidays). Subjects should be placed back on study therapy within 3 weeks of the scheduled interruption. The reason for interruption should be documented in the patient's study record.

Table 1: Dose Modification Guidelines for Drug-Related Adverse Events, version 10-22-2017

General instructions:				
Immune-related AEs	Toxicity grade or conditions (CTCAEv4.0)	Action taken to pembrolizumab	irAE management with corticosteroid and/or other therapies	Monitor and follow-up
Pneumonitis	Grade 2	Withhold	
 Administer corticosteroids (initial dose of 1-2 mg/kg prednisone or equivalent) followed by taper 	
 Monitor participants for signs and symptoms of pneumonitis Evaluate participants with suspected pneumonitis with radiographic imaging and initiate corticosteroid treatment Add prophylactic antibiotics for opportunistic infections
	Grade 3 or 4, or recurrent Grade 2	Permanently discontinue		
Diarrhea / Colitis	Grade 2 or 3	Withhold	
 Administer corticosteroids (initial dose of 1-2 mg/kg prednisone or equivalent) followed by taper 	
 Monitor participants for signs and symptoms of enterocolitis (i.e., diarrhea, abdominal pain, blood or mucus in stool with or without fever) and of bowel perforation (i.e., peritoneal signs and ileus). Participants with \geq Grade 2 diarrhea suspecting colitis should consider GI consultation and performing endoscopy to rule out colitis. Participants with diarrhea/colitis should be advised to drink liberal quantities of clear fluids. If sufficient oral fluid intake is not feasible, fluid and electrolytes should be substituted via IV infusion.
	Grade 4	Permanently discontinue		
AST / ALT elevation or	Grade 2	Withhold	
 Administer corticosteroids (initial dose of 0.5- 1 mg/kg prednisone or equivalent) followed by taper 	
 Monitor with liver function tests (consider weekly or more frequently until liver enzyme value returned to baseline or is

Immune-related AEs	Toxicity grade or conditions (CTCAEv4.0)	Action taken to pembrolizumab	irAE management with corticosteroid and/or other therapies	Monitor and follow-up

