Increased bilirubin	Grade 3 or 4	Permanently discontinue	
 Administer corticosteroids (initial dose of 1-2 mg/kg prednisone or equivalent) followed by taper 	stable
Type 1 diabetes mellitus (T1DM) or Hyperglycemia	Newly onset T1DM or Grade 3 or 4 hyperglycemia associated with evidence of β -cell failure	Withhold	
 Initiate insulin replacement therapy for participants with T1DM Administer anti-hyperglycemic in participants with hyperglycemia 	
 Monitor participants for hyperglycemia or other signs and symptoms of diabetes.
Hypophysitis	Grade 2	Withhold	
 Administer corticosteroids and initiate hormonal replacements as clinically indicated. 	
 Monitor for signs and symptoms of hypophysitis (including hypopituitarism and adrenal insufficiency)
	Grade 3 or 4	Withhold or permanently discontinue ¹		
Hyperthyroidism	Grade 2	Continue	
 Treat with non-selective beta-blockers (e.g., propranolol) or thionamides as appropriate 	
 Monitor for signs and symptoms of thyroid disorders.
	Grade 3 or 4	Withhold or permanently discontinue ¹		
Hypothyroidism	Grade 2-4	Continue	
 Initiate thyroid replacement hormones (e.g., levothyroxine or liothyroinine) per standard of care 	
 Monitor for signs and symptoms of thyroid disorders.
Nephritis and Renal dysfunction	Grade 2	Withhold	
 Administer corticosteroids (prednisone 1-2 mg/kg or equivalent) followed by taper. 	
 Monitor changes of renal function
	Grade 3 or 4	Permanently discontinue		
Myocarditis	Grade 1 or 2	Withhold	
 Based on severity of AE administer corticosteroids 	
 Ensure adequate evaluation to confirm etiology and/or exclude other causes

Immune-related AEs	Toxicity grade or conditions (CTCAEv4.0)	Action taken to pembrolizumab	irAE management with corticosteroid and/or other therapies	Monitor and follow-up
	Grade 3 or 4	Permanently discontinue		

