4 CONCOMITANT MEDICATIONS/MEASURES

All routine and appropriate supportive care (including blood products) will be provided during this study, as clinically indicated, and in accordance with the standard of care practices. Clinical judgment should be utilized in the treatment of any AE experienced by the patient.

Information on all concomitant medications, administered blood products, as well as interventions occurring during the study must be recorded on the patient's eCRF.

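### Section 6.1 leaves every Grade 1 adverse event unrecorded, so a Grade 1 event that changes how study drug is given can be missing from the safety tables

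*Combined protocol and SAP*

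**What the plan says.** Section 6.1 sets the period for documenting adverse events, lists when an abnormal laboratory value counts as one, and then closes the topic with an unconditional sentence: "Grade 1 adverse events will not be recorded".

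Section 8 describes the safety analysis: "adverse events will be tabulated by grade according to CTCAE and analyzed and reported descriptively". It states no lowest grade. Section 1.1.2 makes safety, tolerability and feasibility of the three-drug combination a secondary objective.

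Two treatment rules bear on this:

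- Table 1 in Section 3.4.6 contains the row "Myocarditis Grade 1 or 2 Withhold", where the action is on pembrolizumab.
- The table in Section 3.4.5.1.1 responds to acute laryngopharyngeal dysesthesia by extending the next oxaliplatin infusion to 6 hours. The grade column is empty for that row. Section 3.4.5.2 repeats the 6-hour rule, also without a grade.

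**The concern.** The protocol treats at least one Grade 1 event as reason enough to interrupt a study drug, while its data rule keeps Grade 1 events out of the adverse event record. Staff who follow both instructions would hold a dose and enter no adverse event to explain it. For the oxaliplatin reaction, the outcome depends on the grade the investigator assigns, because the rule that changes the infusion does not ask for one.

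What is at stake is the completeness of the safety tables. In a small single-arm trial of a combination, the events that change administration of study drug are the ones a reader most needs in order to judge tolerability and feasibility. If some are left out by rule, the tables cannot be reconciled with the dosing record.

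**Working it through.** No arithmetic applies: the plan states no figure here to reproduce. The check is whether a Grade 1 event that changes study drug has any route into the adverse event data.

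**Step 1. Where can a Grade 1 event change study drug?**

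| Rule | Effect at Grade 1 |
|---|---|
| Table 1, myocarditis | Pembrolizumab withheld |
| Table 1, other rows | None names Grade 1; the catch-all row starts at intolerable or persistent Grade 2. New-onset type 1 diabetes is listed without a grade |
| Section 3.4.3, hematologic | Table starts at Grade 2 |
| Section 3.4.4, hand-foot syndrome | Rules start at Grade 2 |
| Section 3.4.5.1.1, neuropathy | No dose reduction |
| Section 3.4.5.1.1 and 3.4.5.2, acute laryngopharyngeal dysesthesia | No grade given; next infusion lengthened from 2 to 6 hours |
| Section 3.4.5.3, oxaliplatin hypersensitivity | No dose modification required; premedication suggested |
| Table 2, pembrolizumab infusion reaction | Interruption not indicated |

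One row names Grade 1 and acts on pembrolizumab. One oxaliplatin rule acts whatever the grade.

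**Step 2. Does any other text put such an event, with its grade, into the adverse event data?**

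- *Laboratory list, Section 6.1.* One criterion is "Requires treatment or any other therapeutic intervention". The list concerns laboratory values only, and the Grade 1 sentence follows it with no carve-out.
- *Dosing interruptions, Section 3.4.6.* The text says "The reason for interruption should be documented", but that paragraph is about interruptions unrelated to study therapy.
- *Section 4.* "Information on all concomitant medications, administered blood products, as well as interventions occurring during the study must be recorded" on the eCRF. This could show a corticosteroid given for the event, but it does not ask for the event term or grade.
- *Section 7.5.2.* Reports to the collaborator cover serious events only.
- *Section 7.4.* The principal investigator reviews adverse event data on each patient. That review does not create a record that Section 6.1 rules out.

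No text requires a non-serious Grade 1 event that led to a hold or a longer infusion to be entered as an adverse event.

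**Step 3. What reaches Section 8?** If Section 6.1 is followed as written, the Grade 1 category is empty by rule. A non-serious Grade 1 myocarditis that caused a hold is not in the tables. A laryngopharyngeal reaction that changed the infusion is in them only if graded 2 or higher or otherwise captured as serious.

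**The case against.** The strongest reply is that the recording threshold nearly matches the action thresholds. As Step 1 shows, Grade 1 is almost everywhere the level at which nothing is done, so leaving routine Grade 1 events unrecorded is a reasonable saving of effort. That stands, and the point does not challenge it.

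It can also be said that the exception is unlikely to matter in practice. The Study Calendar schedules an EKG only at screening and baseline, and its chemistry panel lists no cardiac marker, so a mild myocarditis might not be found. Corticosteroids given for it would appear among concomitant medications. Safety is descriptive, with no test or threshold attached. These arguments limit the weight of the point. They do not supply a route for the event and its grade into the adverse event data.

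Three stronger readings are tempting, and the documents do not support them:

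- A reader might see a contradiction within Section 6.1, because adverse events "regardless of severity, will be followed until return to baseline or stabilization of event". That sentence governs how long events are followed; the Grade 1 sentence governs what is entered. An event can be followed clinically without being entered.
- A reader might infer that any-grade incidence will be understated. Section 8 does not promise any-grade incidence, and a table of Grades 2 to 5 is still a table by grade. What is missing is a statement of scope.
- A reader might take one patient in the accrual ceiling of 19, 1/19 = 5.3%, as the size of the loss. That is only the weight of one patient if an event occurs. The documents give no rate from which an expected loss could be calculated.

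**Conclusion.** The point holds in a narrow form. The recording rule has no exception for Grade 1 events that alter study drug administration, and the protocol provides for at least one: Grade 1 myocarditis. Acute laryngopharyngeal dysesthesia is a second possibility, on the assumption that an investigator may grade some episodes as 1; the documents do not say how such episodes are graded. A non-serious event of either kind can be missing from the safety tables, with at most an indirect trace in concomitant medication, intervention or dosing records.

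Its size in patients cannot be stated from the documents. It does not touch the 5-month progression-free endpoint, the two-stage decision or the sample size. It merits correction because the safety tables serve a stated objective and the change is cheap.

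**What to change.** Amend Section 6.1 so that a Grade 1 event is recorded when it leads to a hold, delay, infusion change or discontinuation of any study drug, or when Table 1 lists it for action. State in Section 8, and in the table titles, that the adverse event tables cover Grade 2 or higher plus treatment-modifying Grade 1 events.

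The cost is a few extra CRF entries and a change of table title. Routine Grade 1 events stay unrecorded. The amendment concerns data collection and reporting only: Table 1, the oxaliplatin rules, the sample size and the stopping boundary remain as they are.
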